### 2.7.4 Other safety data

### 2.7.4.1 ECG and cardiac imaging data

The number and percentage of participants with an abnormal ECG (clinically significant) at screening will be presented. A listing of all ECG assessments will be produced. These analyses will be performed for the FAS.

# 2.7.4.2 Vital signs

Vital sign assessments are performed in order to characterize basic body function. The following parameters were collected: body temperature, blood pressure, heart rate, respiratory rate.

### **Data handling**

Vital signs collected prior to (baseline), and within 14 days (+ 3 day-window) after each imaging agent administration (and prior to the subsequent imaging agent administration, if applicable) will be summarized. Values measured outside of the on-treatment period will be flagged in the listings.

### **Data analysis**

For analysis of vital signs, the clinically notable vital sign criteria are provided in Table 2-2 below.

Table 2-2 Clinically notable changes in vital signs

Vital sign (unit)	Clinically notable criteria	
	Increase	Decrease
Systolic blood pressure (mmHg)	>=180 with increase from baseline of >=20	<=90 with decrease from baseline of >=20
Diastolic blood pressure (mmHg)	>=105 with increase from baseline of >=15	<=50 with decrease from baseline of >=15
Body temperature (°C)	>= 39.1	-
Pulse rate (bpm)	> 100 with increase from baseline of > 25%	< 60 with decrease from baseline > 25%
Respiratory rate	> 22 breaths per minute	<14 breaths per minute

The number and percentage of participants with notable vital sign values (high/low) will be presented. Descriptive statistics will be tabulated for baseline, at each post-baseline time point and changes from baseline at each post-baseline time point for each vital sign measure.

A listing of all vital sign assessments will be produced by treatment sequence and notable values will be flagged. In the listing, the assessments collected outside of on-treatment period will be flagged.

# 2.8 Pharmacokinetic endpoints

No pharmacokinetic endpoints are defined in the study.

# 2.9 PD and PK/PD analyses

[figure not shown]
No PD and PK/PD analyses are planned in the study.

## 2.10 Patient-reported outcomes

No patient-reported outcomes analyses are planned in the study.

## 2.11 Biomarkers

No biomarker analyses are planned in the study.

# 2.13 Interim analysis

No interim analysis is planned for this study.

# 3 Sample size calculation

Overall, approximately 190 participants will be enrolled to ensure at least 152 participants are evaluable (i.e. those who have both an evaluable [18F]CTT1057 PET/CT scan imaging, and at least one evaluable CTS assessment and have not received any prohibited systemic antineoplastic therapy before the completion of PET/CTs and CTS procedures), which will be required for the calculation of the co-primary endpoints. These calculations were made using the software PASS 11 and R 3.6.1.

# 3.1 Primary endpoints(s)

This study is planned to recruit approximately 190 participants. The sample size calculation is based on the co-primary endpoints of region-level CLR and the patient-level PPV of [18F]CTT1057.

The assumptions for sample size calculations are based on the estimates from data available from prior studies.

The primary endpoint is to evaluate region-level CLR (prostate region, PLN, extra-pelvic lymph nodes, skeletal, and visceral) and patient-level PPV of [F]CTT1057 PET for detection of tumor location confirmed by CTS. Based on the results of previous studies, the following distribution of disease across regions are anticipated: Prostate bed: 30%, pelvis: 15%; extrapelvic soft tissue: 20%; bone metastases: 35% (Eiber et al 2015, Ceci et al 2015, Van Leeuwen et al 2016). It is anticipated that the CLR for the five regions and for all regions combined using conventional imaging ranges from 30-60%. An overall CLR for [F]CTT1057 PET of at most 50% will be considered as unacceptably low. Hence, the null hypothesis that the CLR is at most 50% will be tested against the alternative hypothesis that the CLR is greater than 50%.

The BCR population targeted in this study is expected to have similar PSA values as prior studies (Morris et al 2020) of approved diagnostic PET agents for PCa such as [F]-fluciclovine, which had a 27% PPV for patients with PSA values that were less than 1.78, as noted in their summary basis of approval. Thus, a patient-level PPV of 20% will be considered as unacceptably low. The [F]CTT1057 positive patient rate (detection rate) for the study population is 80% based on [F]-fluciclovine studies. The sample size calculation will be performed based on the null and alternative hypotheses as follows.

#### **Region-level CLR**

Correlated binary test results occur in this situation where each experimental unit (participant) consists of five correlated regions. Lee and Dubin developed a sample size formula for clustered binary data (Lee and Dubin 1994). They propose estimating the binary proportion by assigning equal weights to clusters regardless of their sizes to simplify the derivation of their sample size

formula. The weighted estimator for region-level CLR is approximately Gaussian distributed with a variance of a beta distribution (beta-binomial model).

The null hypothesis (H0: region-level CLR p = 0.50) will be tested against the alternative hypothesis (H1: p > 0.50). Assuming a CLR of 0.58 under the alternative hypothesis, a total sample size of 172 enrolled participants would achieve 90% statistical power to detect a change in CLR of 0.08 using a one-sided test at a target significance level of 2.5%. This sample size includes an adjustment for a dropout rate of 20%.

The sample size was determined as n to ensure a type I error using a one-sided significance level of 2.5% and with 90% power to reject H0 if the alternative H1 is true.

By the standard normal approximation, the sample size is given as follows:

$$n = \frac{\sigma^2 (Z_{\alpha} - Z_{1-\beta})^2}{(p_1 - p_0)^2}$$

where  $\sigma^2$  is the variance of a beta distribution,  $Z_a$  is the upper quantile of the standard normal distribution,  $p_0$  is a CLR of 0.50 under the null hypothesis, and  $p_1$  is a CLR of 0.58 under the alternative hypothesis.

Suppose there is no information on the within-cluster correlation of test results. In this case, a uniform distribution seems reasonable, setting parameters in the beta distribution of alpha=1 and beta=1. Then  $\sigma^2$  is 1/12.

Under these assumptions, 137 participants will be necessary to ensure 90% power. Taking into account a 20% dropout rate, a total of 172 participants will be recruited for this endpoint of the study.

The lower bound of the 95% CI for CRL should be greater than 0.50 to be considered a success.

#### **Patient-level PPV**

The null hypothesis (H0: patient-level PPV p = 0.20) will be tested against the alternative hypothesis (H1: p > 0.20). Assuming a patient-level PPV of 0.33 under the alternative hypothesis, a total sample size of 190 enrolled participants (which includes 152 [ $^{18}$ F]CTT1057 scanned participants based on 80% [ $^{18}$ F]CTT1057 positive patient rate) would achieve 90% power to detect a change in patient-level PPV of 0.13 using a one-sided binomial test at a targeted significance level of 2.5%. This sample size includes an adjustment for a dropout rate of 20%.

The lower bound of the 95% CI for patient-level PPV should be greater than 0.20 to be considered a success.

A total sample size of 190 participants can ensure 92.7% statistical power for region-level CLR and 90% statistical power for patient-level PPV resulting in an overall study statistical power of at least 83.4% (0.927\*0.90).

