Correlated binary test results occur in this situation where each experimental unit (patient) consists of five correlated regions. Lee and Dubin developed a sample size formula for clustered binary data (Lee and Dubin 1994). They propose estimating the binary proportion by assigning equal weights to clusters regardless of their sizes to simplify the derivation of their sample size formula. The weighted estimator for region-level CLR is approximately Gaussian distributed with a variance of a beta distribution (beta-binomial model).

The null Hypothesis H0: region-level CLR p = 0.5 will be tested against the alternative hypothesis H1: p > 0.5 Assuming a CLR of 0.58 under the alternative hypothesis, a total sample size of 172 enrolled participants would achieve 90% statistical power to detect a change in CLR of 0.08 using a one-sided test at a target significance level of 2.5%. This sample size includes an adjustment for a dropout rate of 0.20.

To determine the sample size n such that the type I error of one-sided testing H0 is 0.025 and with power 0.9 to reject H0 if alternative H1 is true. By the standard normal approximation, the sample size is given

Amended Protocol (Version No. 01 Clean)

$$n = \frac{\sigma^2 (Z_{\alpha} - Z_{1-\beta})^2}{(p_1 - p_0)^2}$$

where σ^2 the variance of a beta distribution, Z_a is the upper a quantile of the standard normal distribution, p_0 is the CLR 0.5 under null hypothesis, p_1 is 0.58 the achievable CLR.

Suppose there is no information on the within-cluster correlation of test results. In this case, a uniform distribution seems reasonable, setting parameters in the beta distribution alpha=1 and beta=1. Then σ^2 is 1/12

Under these assumptions, 137 patients will be necessary to ensure the 90% power, taking into account 20% dropout rate, a total of 172 patients will be recruited for this endpoint of the study.

The lower bound of the 95% CI for CRL should be greater than 0.5 to be considered success.

• Patient-level PPV

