An individual PET reader will be considered successful if he/she meets the predefined thresholds for both co-primary endpoints, and at least two of three readers should be successful for overall study positivity.

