#### 2.5.5 Sensitivity analyses

For participants where CTS Level 1 or 2 is used as the truth standard for the primary analysis, the next lower level of CTS will be used to verify positivity or negativity for the sensitivity analysis, if available. For instance, if pathology (CTS Level 1) is used for a lesion as the truth standard for the primary estimand, the imaging component of CTS (Level 2) will be used as truth standard for sensitivity analysis for the primary estimand. Similarly, results of CTS Level 2 will be replaced by CTS Level 3 if applicable. However, for those using changes in PSA level (CTS Level 3) as the truth standard for primary estimand, their positivity status cannot be replaced by another component of CTS for sensitivity analysis.

Region-level CLR along with its 95% CI will also be computed based on the weighted estimator approach (Lee and Dubin 1994) for each central reader as following:

$$\hat{p}_w \pm 1.96 \hat{\sigma}/\sqrt{n}$$
.

 $\hat{p}_w$  is the point estimator with  $\hat{p}_w = \sum_{i=1}^n \hat{p}_i / n$  and  $\hat{p}_i = y_i / n_i$ , where  $y_i$  and  $n_i$  are the same as defined in Section 2.5.2 above and n represents the number of participants with at least one PET-positive finding by central assessments.  $\hat{\sigma}$  is the estimated standard deviation of  $\hat{p}_i$ .

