#### 5.4 Statistical models

## 5.4.1 Analysis supporting primary objective(s)

For region-level CLR, statistical model details are presented in Section 2.5. The GLIMMIX procedure in SAS will be used to implement the logistic regression model with random effects.

This analysis will be restricted to participants with at least one PET positive region (TP or FP) by central assessments in the EFF. In case of problems with fitting the model and estimating parameters, the default estimation technique (i.e. residual pseudo-likelihood with a subject expansion (METHOD = RSPL)) will be used. This analysis will be applied to each of the three central readers via the (BY READER) statement.

For this model, the SAS code will be:

```
proc glimmix data=dataset;
by reader;
  class subject;
  model tpcount / poscount= / solution;
  random intercept / subject=subject;
run;
```

- tpcount refers to the number of TP regions per participant
- poscount refers to the number of PET positive regions (TP or FP) per participant

The estimated fixed effect  $\hat{\mu}$  and its standard error SE on the logit scale can be obtained from the output. And the (subject-specific) region-level CLR (conditional on the random effect when  $b_i = 0$ ) along with the two-sided 95% CI can be computed by applying the inverse link function:

Point estimate of the region-level CLR: 
$$E[p_{i}|\hat{b}_{i}=0] = E\left[\frac{y_{-}i}{n_{-}i}|\hat{b}_{i}=0\right] = \frac{\exp(\hat{\mu})}{1+\exp(\hat{\mu})}$$

$$CI_{Lower} = \frac{\exp(\hat{\mu}-z_{0.975}SE)}{1+\exp(\hat{\mu}-z_{0.975}SE)}$$

$$CI_{Upper} = \frac{\exp(\hat{\mu}+z_{0.975}SE)}{1+\exp(\hat{\mu}+z_{0.975}SE)}$$

For patient-level PPV, an exact binomial confidence interval (implemented using SAS procedure FREQ with EXACT statement for one-way tables) will be calculated (Clopper and Pearson 1934)

[figure not shown]
Efficacy endpoints be summarized in terms of percentage rates with 95% CIs.

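### The 92.7% CLR power does not follow from the plan's own beta-binomial model and analysis population, and the 83.4% overall figure is a single-reader product

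*SAP*

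**What the plan says.** Region-level CLR is sized with an equal-weight cluster estimator. The null is 0.50, the alternative 0.58, with a one-sided 2.5% test. Having no information on within-participant correlation, the SAP says "a uniform distribution seems reasonable, setting parameters in the beta distribution of alpha=1" (and beta = 1), takes the variance as 1/12, and concludes: "Under these assumptions, 137 participants will be necessary to ensure 90% power". Dropout of 20% brings this to 172 enrolled. Protocol 12.8.1 has the same text: "a uniform distribution seems reasonable, setting parameters in the beta distribution alpha=1 and beta=1".

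For the full enrolment (152 evaluable), the SAP then states: "A total sample size of 190 participants can ensure 92.7% statistical power for region-level CLR and 90% statistical power for patient-level PPV". It gives an overall power of at least 83.4% as 0.927 × 0.90.

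Four other statements bear on this:

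- SAP 3.1: the "positive patient rate (detection rate) for the study population is 80" per cent.
- SAP 2.5.5, defining the weighted estimator as the mean of y_i/n_i: "n represents the number of participants with at least one PET-positive finding by central assessments".
- SAP 5.4.1, on the primary CLR model: "restricted to participants with at least one PET positive region (TP or FP) by central assessments".
- SAP 2.5.2, on success: each reader must meet both thresholds, and "at least two of three readers should be successful for overall study positivity".

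**The concern.** Three things do not fit together.

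- **Variance.** The plan names a beta-binomial model but uses only the beta part. The data are observed proportions from at most five regions, so binomial error cannot be neglected.
- **Denominator.** CLR and PPV are both analysed in PET-positive participants, yet the 80% positive rate was applied to PPV and not to CLR.
- **Success rule.** The overall figure is a product for one reader, while success is defined over three. The product also pairs a PPV alternative with a CLR alternative that cannot both hold for the estimator used for sizing.

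CLR is the harder of the two co-primaries at the planning alternative. If its power is overstated, readers of the plan will overestimate the chance of success, and a missed CLR could be taken as evidence against the agent when it may reflect imprecision.

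**Working it through.** **1. Reproducing the plan.** With σ² = 1/12 and a difference of 0.08:

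- n = (1/12)(1.96 + 1.2816)²/0.08² = 136.8, so 137; 137/0.8 = 171.25, so 172.
- Power at n = 152: Φ(0.08·√(152 × 12) − 1.96) = 0.927.
- 0.927 × 0.90 = 0.834.

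The arithmetic is right, so the 92.7% rests on both σ² = 1/12 and n = 152.

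**2. Variance.** Under Beta(1,1), Var(p_i) = 1/12 and E[p_i(1 − p_i)] = 1/6, so with m PET-positive regions

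Var(y_i/m) = 1/12 + (1/6)/m = 0.25[1 + (m − 1)/3]/m.

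The implied within-participant correlation is 1/3. The variance is 0.25 for m = 1 and 0.117 for m = 5, the maximum. It is never 0.083.

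**3. Denominator.** 152 × 0.80 = 121.6, about 122 PET-positive participants, which is below the 137 called necessary. The PPV figure shows that the plan used this count there. Exact binomial power at 0.33 against 0.20 is 90.5% at n = 122 (cut-off 34) and 95.4% at n = 152 (cut-off 41); the plan states 90%. Changing only n for CLR gives Φ(0.08·√(121.6 × 12) − 1.96) = 0.863.

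**4. CLR power at 0.58, per reader.** The documents do not give m. The regional shares of 30, 15, 20 and 35% sum to 100% and say nothing about the number per participant. So m = 1 to 5 is an assumed range.

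| m | n = 152, variance corrected | n = 121.6, variance at 0.50 | n = 121.6, variance at 0.58 |
|---|---|---|---|
| 1 | 50.5% | 42.2% | 43.1% |
| 2 | 67.6% | 58.0% | 59.1% |
| 3 | 75.4% | 65.8% | 66.9% |
| 4 | 79.7% | 70.4% | 71.5% |
| 5 | 82.3% | 73.3% | 74.4% |

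Simulation with mean 0.58, correlation 1/3 and 122 participants gives 45, 59, 66, 71 and 74% for the SAP 2.5.5 interval. The random-intercept logistic model gives 58, 65 and 72% for m = 2, 3 and 5. At m = 1 the random-intercept variance is not identifiable, and plain logistic regression gives 45%.

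With 121.6 participants, 90% per-reader power holds at a true CLR of about 0.64–0.65 (m = 1), 0.62 (m = 2), 0.61 (m = 3) or 0.60 (m = 4 or 5).

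**5. The product.** A participant's indicator of at least one true-positive region is never smaller than y_i/n_i. An equal-weight CLR of 0.58 therefore implies PPV ≥ 0.58, where PPV power at n = 122 exceeds 0.9999. Multiplying by power at PPV = 0.33 is incoherent, and it makes the product too low. This need not hold for a CLR pooled over regions: 40 participants with 5/5 and 82 with 0/1 give a pooled CLR of 200/282 = 0.71 with a PPV of 40/122 = 0.33.

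**6. Reader rule.** With PPV power near 1, per-reader success is essentially CLR power p. For independent readers, two-of-three power is 3p² − 2p³: 0.38 at p = 0.42 and 0.837 at p = 0.744. With an assumed latent between-reader correlation of 0.5 it is 0.41 and 0.78; with identical readers it equals p. Reaching 0.834 with independent readers needs p = 0.741, which occurs only at m = 5 in every participant.

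**The case against.** **The correlation of 1/3 is inferred, not stated.** The SAP says it has no information and uses the uniform as a stand-in. Power depends on correlation as much as on region count. At n = 121.6, for m = 1 to 5, it is 42/70/86/94/98% at correlation 0, 42/66/80/87/92% at 0.1 and 42/53/58/61/63% at 0.5. On this view 1/12 could be the assumed total variance of the participant proportion, and the text does attach the beta variance to the weighted estimator itself. This stands as a caution: 42–74% is what the plan's stated distribution implies, not a forecast. It does not rescue 92.7%. A total variance of 1/12 needs at least three PET-positive regions in every participant, with correlation 0 (three), 0.11 (four) or 0.17 (five). The plan assumes none of these, and Beta(1,1) fixes 1/3. Even granting 1/12, the denominator error leaves 86%.

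**The other faults do not all point downwards.** This is correct. The PPV mismatch makes the product too low. If per-reader power really were 83.4%, the two-of-three rule would give 92.6% with independent readers and 83.4% with identical ones. The denominator error alone need not break 83.4%: CLR power of 86% with PPV power near 1 still exceeds it, although keeping the plan's 0.90 gives 0.863 × 0.90 = 77.7%. The overstatement comes from the variance and denominator together.

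**Planning power enters no test, and the SAP is at the database-lock stage.** This is true, and it is why the remedy is confined to wording. The figure still stands in both documents as a claim about what the design delivers.

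**Conclusion.** The concern holds. The 92.7% is computed correctly from the printed formula, but the formula's two inputs conflict with the plan's own model and analysis population. Correcting both gives per-reader CLR power at 0.58 of about 42% to 74%, and no region count from one to five reaches 92.7%. Those figures assume the plan's Beta(1,1), its 80% positive rate, 152 evaluable participants and an equal region count across participants. The shortfall within that range cannot be fixed from the documents.

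The 83.4% is not the power of the stated success rule. Over the same range, two-of-three power is 38–84% with independent readers, 41–78% at a latent correlation of 0.5 and 42–74% with identical readers. The reader correlations are assumptions, because the plan gives none.

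**What to change.** In SAP 3.1 and protocol 12.8.1:

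- Replace σ² = 1/12 with Var(y_i/n_i) = π(1 − π)[1 + (n_i − 1)ρ]/n_i, stating both ρ and the assumed distribution of PET-positive regions per participant.
- Use about 122 PET-positive participants for CLR, as was done for PPV.
- Restate per-reader CLR power as a range conditional on those assumptions (about 42–74% at 0.58 under Beta(1,1)), or give the CLR at which 90% power holds (about 0.60–0.65).
- Choose a PPV alternative compatible with the CLR alternative.
- Remove the 83.4%, or recompute it under the two-of-three rule with a stated between-reader correlation.

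Only wording changes: enrolment, thresholds and analysis are untouched. The cost is a less favourable power statement.

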# 4 Change to protocol specified analyses

The subgroup analyses on participants with prior RP and participants with prior curative intent RT will be applied to co-primary and secondary efficacy endpoints only.

Minor updates to the estimand wording were made as compared to the protocol for clarification.

# 5 Appendix

# 5.1 Imputation rules

# 5.1.1 Study drug

The complete date of dose administration is required for this study. Completely or partially missing date will not be imputed and should be considered as a data issue and the statistician should contact the data manager of the study.

# 5.1.2 AE, ConMeds and safety assessment date imputation

Table 5-1 Imputation of start dates (AE, CM) and assessments (LB, EG, VS)

Missing	Rule
Element	
day, month, and year	No imputation will be done for completely missing dates
day, month	
 
If available year = year of study treatment start date then         
 
If stop date contains a full date and stop date is earlier than study treatment start date then set start date = 01JanYYYY
 
Else set start date = study treatment start date.
 
 
 
If available year > year of study treatment start date then 01JanYYYY
 
If available year < year of study treatment start date then 01JulYYYY
 

Missing	Rule
Element	
day	
 
If available month and year = month and year of study treatment start date then
 
If stop date contains a full date and stop date is earlier than study treatment start date then set start date= 01MONYYYY.
 
Else set start date = study treatment start date.
 

	
 
If available month and year > month and year of study treatment start date then 01MONYYYY
 
If available month and year < month year of study treatment start date then 15MONYYYY
 

Table 5-2 Imputation of end dates (AE, CM)

Missing	Rule	
Element	(*=last study treatment date plus 15 days not > (death date, cut-off date,	
	withdrawal of consent date))	
day, month, and year	• Completely missing end dates (incl. ongoing events) will be imputed by the end date of the on-treatment period*	
day, month	• If partial end date contains year only, set end date = earliest of 31DecYYYY or end date of the on-treatment period *	
day	• If partial end date contains month and year, set end date = earliest of last day of the month or end date of the on-treatment period*	

If imputed end date < start date, set end date = start date.

Any AEs and ConMeds with partial/missing dates will be displayed as such in the data listings.

Any AEs and ConMeds which are continuing as per data cut-off will be shown as 'ongoing' rather than the end date provided.

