#### Study day

The study day describes the day of the event or assessment date, relative to the reference start date.

The study day is defined as:

- The date of the event (visit date, onset date of an event, assessment date etc.) reference start date + 1 if event is on or after the reference start date;
- The date of the event (visit date, onset date of an event, assessment date etc.) reference start date if event precedes the reference start date.

The reference date for all assessments (safety, efficacy, etc) is the start of study treatment.

The study day will be displayed in the data listings. If an event starts before the reference start date, the study day displayed on the listing will be negative.

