#### **Baseline**

For safety evaluations, the last available assessment on or before the date/time of start of study treatment [18F]CTT1057 is defined as "baseline" assessment for [18F]CTT1057 safety.

The last available assessment on or before the date/time of start of study treatment [Ga]Ga-PSMA-11 is defined as "baseline" assessment for [Ga]Ga-PSMA-11 safety.

If participants have no value as defined above, the baseline result will be set to missing.

Efficacy evaluations will not include any comparisons between baseline and post-baseline values, and therefore a baseline definition for efficacy evaluations does not apply.

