#### Windows for multiple assessments

In order to summarize weight, vital signs, and laboratory tests collected over time (including unscheduled visits), the assessments will be time slotted. The following general rule will be applied in creating the assessment windows: If more than one assessment is done within the same time window, the assessment performed closest to the target date will be used. If 2 assessments within a time window are equidistant from the target date, then the earlier of the 2 assessments will be used. If there are multiple assessments on the same date then the worst case value will be used. Data from all assessments (scheduled and unscheduled), including multiple assessments, will be listed.

For participants randomized into sequence 1: [18F]CTT1057 - [68Ga]Ga-PSMA-11

Time Window	Planned Visit Timing	Time Window Definition
On treatment		
Baseline for [18F]CTT1057	On or before Study Day 1*	≤ Study Day 1, and time prior to [  F]CTT1057 injection
Day 1 for [18F]CTT1057	Study Day 1	Date of [18F]CTT1057 injection
Day 15 for PET for [18F]CTT1057	Study Day 15	Study Day 15 - 22, and time prior to [  Ga]Ga-PSMA-11 injection
Baseline (Day 1) for [68Ga]Ga-PSMA-11	On or before [  Ga]Ga-PSMA-11 injection and after [  F]CTT1057 injection	≥Study Day 15 and ≤ Study Day 22, time prior to [  Ga]Ga-PSMA-11 injection
Day 1 for [  Ga]Ga- PSMA-11	On [  Ga]Ga-PSMA-11 injection	Date of [  Ga]Ga-PSMA-11 injection

\*Study Day 1 = the date of [18F]CTT1057 injection

For participants randomized into sequence 2: [68Ga]Ga-PSMA-11 - [18F]CTT1057

Time Window	Planned Visit Timing	Time Window Definition	
On treatment			
Baseline for [  Ga]Ga- PSMA-11	On or before Study Day 1*	≤ Study Day 1, and time prior to [  Ga]Ga-PSMA-11 injection	
Day 1 for [  Ga]Ga- PSMA-11	Study Day 1	Date of [  Ga]Ga-PSMA- 11injection	
Day 15 for PET for [  Ga]Ga-PSMA-11	Study Day 15	Study Day 15 - 22, time prior to [  F]CTT1057 injection	
Baseline for [18F]CTT1057	On or before [  F]CTT1057 and after [  Ga]Ga-PSMA-11	≥Study Day 15 and ≤ Study Day 22, time prior to [18F]CTT1057 injection	
Day 1 for [18F]CTT1057	On [18F]CTT1057 injection	Date of [  F]CTT1057 injection	
Day 15 for [18F]CTT1057	the date of [18F]CTT1057 injection + 14 days	Study Day 29-39	

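### SAP Table 5-1 applies an adverse-event start-date rule to laboratory and vital-sign dates, so a post-dose sample with a missing day is usually moved out of its visit window and can be counted under the wrong tracer

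*SAP*

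**What the plan says.** SAP 5.1.2 gives one table for adverse-event and concomitant-medication start dates and for assessment dates: "Imputation of start dates (AE, CM) and assessments (LB, EG, VS". When only the day is missing and the month is that of the study treatment start, an exception applies if there is a full stop date earlier than treatment start. Otherwise the instruction is "Else set start date = study treatment start date". When the recorded month is later, the result is the first of that month: "month and year of study treatment start date then 01MONYYYY".

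The placement rules are in SAP 2.1.1:

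- **Study day:** "The reference date for all assessments (safety, efficacy, etc) is the start of study treatment".
- **Safety baseline for each tracer:** "the last available assessment on or before the date/time of start of study treatment" with that tracer.
- **First tracer's baseline slot:** "≤ Study Day 1, and time prior to" its injection.
- **First tracer's Day 15 slot:** "Study Day 15 - 22", before the second injection. The second tracer's baseline slot uses the same day range.
- **Ties:** "If there are multiple assessments on the same date then the worst case value will be used".

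SAP 2.7.3 (laboratory) and 2.7.4.2 (vital signs) summarise values taken within 14 days (+3) after each tracer and before the next one. SAP 5.1.1 treats dose dates differently: they are never imputed, and an incomplete one is handled as a data issue.

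**The concern.** Moving an adverse event to the earliest compatible date is cautious, because it favours calling the event treatment-emergent. An assessment is a measurement at one time point. It has no stop date, so the exception cannot apply, and moving it earlier changes its order relative to the injections.

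This design is exposed because the sample before the second injection does two jobs. It is the 14-day follow-up for the first tracer (Protocol Table 8-1, footnote 3) and the baseline for the second. Nothing in the SAP exempts imputed assessment dates from baseline selection or slotting, or tells the programmer to use the recorded visit instead. At stake are the by-visit laboratory and vital-sign summaries and the attribution of follow-up values to the right tracer. Protocol 4.1 gives a clean safety profile for each agent as the reason for the two-week gap.

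**Working it through.** The plan states no figure to reproduce. The check applies the missing-day row of Table 5-1 to every possible first-injection date.

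**Inputs.** The rule is from SAP 5.1.2 and the windows from SAP 2.1.1. A 365-day calendar is assumed, with all start dates equally likely. For the Day 29 case the second injection is assumed to fall on Study Day 15.

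**Formula.** A sample on Study Day k is taken k − 1 days after the first injection. In a month of L days it stays in the same month for L − (k − 1) start dates. Summed over 12 months, 365 − 12(k − 1) start dates send it to Study Day 1. This holds for k up to 29, since the shortest month has 28 days. For the other start dates the 1st of the next month falls on Study Day j, with j from 2 to k. Each j occurs once per month, so 12 times a year.

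| True day | Dated to Day 1 | Dated to Days 2–14 | Dated to Day 15 or later |
|---|---|---|---|
| 15 | 365 − 168 = 197 (54.0%) | 13 × 12 = 156 (42.7%) | 12 (3.3%) |
| 22 | 365 − 252 = 113 (31.0%) | 156 (42.7%) | 8 × 12 = 96 (26.3%) |
| 29 | 365 − 336 = 29 (7.9%) | 156 (42.7%) | 15 × 12 = 180 (49.3%) |

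**Loss from the Study Day 15–22 slot.** For a true Day 15 sample it is 353/365 = 96.7%. For a true Day 22 sample it is 269/365 = 73.7%. Averaged over true Days 15 to 22 it is 85.2%. Running the rule over every start date from 2021 to 2023 gives the same shares.

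**Wrong tracer.** A true Day 29 sample is dated before the second injection for (29 + 156)/365 = 50.7% of start dates. For the 156 dated to Days 2–14, the imputed date is 1 to 13 days after the first injection and before the second. SAP 2.7.3 and 2.7.4.2 then place the value under the first tracer.

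**Examples.**
- First injection 10 March, sample 24 March: dated 10 March (Study Day 1).
- First injection 15 March, sample 3 April (Study Day 20): dated 1 April (Study Day 18), still in the slot.
- First injection 20 March, second injection 3 April, follow-up 17 April: dated 1 April (Study Day 13), before the second injection.

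**What follows from each move of a Day 15–22 sample.**
- *Dated to Study Day 1.* It can enter the first tracer's baseline only if its clock time precedes that day's injection, or if a missing time is treated as pre-dose. The SAP does not say how a missing time is handled. If a true pre-dose sample shares the date, the tie rule picks the re-dated value only when it is worse.
- *Dated to Days 2–14.* It stays in the worst on-treatment and shift tables, because SAP 2.7.3 takes all values within the window. It drops out of the by-visit Day 15 summary and out of the second tracer's baseline slot.

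**The case against.** The strongest reply is that the trigger should be rare. Hematology and chemistry go to a central laboratory (Protocol 8.4.1). The Day 15 sample belongs to a visit whose dose date must be complete (SAP 5.1.1). The eCRF has automatic checks, and missing values are queried (Protocol 11.1 and 11.2). ECG is scheduled only at screening, so that part of the rule hardly matters. This stands as a limit on frequency. It does not make the rule right when it is used: vital signs are recorded at the sites, and local laboratory results are combined with central ones (SAP 2.7.3).

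A reader might also infer more than the documents support:

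- *That 54% of such samples are absorbed into baseline and hide a shift.* The 54% is only the share dated to Study Day 1. Entry to baseline also needs the time-of-day condition and, against a true pre-dose sample, a worse value.
- *That the second tracer loses its baseline.* The narrower slot in the windows tables does lose the sample, but the general definition takes the last available assessment and would still supply one. The two provisions differ, and a missing baseline does not follow.
- *That shift tables are generally distorted.* Values of the first tracer moved to Days 2–14 still count in them.
- *That the Day 15 slot is always emptied.* It stays filled for 3.3% of start dates with a Day 15 sample and 26.3% with a Day 22 sample.

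**Conclusion.** The rule is unsuited to assessments as written. Whenever the day is missing from a post-dose laboratory or vital-sign record, it usually puts the value on a wrong study day. For about half of start dates it also places a Day 29 follow-up before the second injection. All percentages are conditional on a partial date and on evenly spread start dates, and the 51% also assumes a second injection on Day 15. The documents do not say how many partial dates to expect. With central laboratory data and routine queries the number is probably small. The effect is confined to descriptive safety summaries, and the co-primary and other efficacy analyses are untouched. This is a minor point, worth correcting because the correction is cheap.

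**What to change.** Remove the laboratory, ECG and vital-sign codes (LB, EG, VS) from the title of Table 5-1 and state that assessment dates are not imputed. Then:

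- Query any partial assessment date as a data issue, as SAP 5.1.1 already does for dose dates.
- Slot scheduled records by their recorded visit and pre- or post-injection time point from Protocol Table 8-1.
- Only list unscheduled records whose partial date cannot be resolved, and never use them as baseline.

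The cost is a short change of SAP wording and minor programming. The downside is that a few undated unscheduled records leave the summaries, though they remain in the listings.
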